3. ANALYSIS SETS

3.1. Intent-to-Treat Analysis Set

The intent-to-treat (ITT) analysis set will include all randomized participants.

In the ITT analysis set, treatment will be assigned based on the treatment to which participants were randomized, regardless of which treatment they actually received.

3.2. Safety Analysis Set

The safety analysis set will include all randomized participants who receive at least 1 dose of IMP.

In the safety analysis set, treatment will be assigned based on the treatment participants actually received, regardless of the treatment to which they were randomized.

3.3. Full Analysis Set

The full analysis set (FAS) will include all participants in the ITT population who receive at least 1 dose of IMP and have at least 10 days of diary entries postbaseline for efficacy assessments on the primary endpoint.

3.4. Per-Protocol Analysis Set

The per-protocol analysis set will consist of all participants in the FAS who have completed the trial without important deviations such as important inclusion/exclusion criteria deviations, important deviations or omissions of the IMP administration, or unexpected drug concentration findings, and who have at least 75% diary compliance after the start of treatment.

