### **6.6.3. Blinding and Unblinding**

Blinded pharmacokinetic data may be assessed during the trial. For participants who have pharmacokinetic sample bioanalysis or data analysis conducted, the individuals responsible for sample bioanalysis and other responsible personnel will know who received test IMP and who received placebo IMP during the trial (of those participants only). Personnel responsible for bioanalysis will be provided with the randomization code to facilitate the analysis. However, the personnel responsible for bioanalysis and pharmacokinetic data analysis will not have access to clinical safety and efficacy data and will provide concentration data to other personnel in a manner that will not identify individual participants (ie, a dummy participant identifier will be linked to the concentration data of an individual participant).

In case of a serious adverse event, pregnancy, or in cases when knowledge of the IMP assignment is needed to make treatment decisions, the Investigator may unblind the participant's IMP assignment as deemed necessary, mainly in emergency situations. Individual randomization codes, indicating the IMP assignment for each randomized participant, will be available to the Investigator(s) or pharmacist(s) at the investigational center via the Randomization and Trial Supply Management system, both via telephone and internet. Breaking of the treatment code can always be performed by the Investigator without prior approval by the Sponsor; however, the Sponsor should be notified following breaking of the treatment code. The participant's IMP assignment should not be revealed to the Sponsor.

When a blind is broken, the participant will be withdrawn from the trial and the event will be recorded on the CRF. The circumstances leading to the breaking of the code should be fully documented in the Investigator's trial files and in the participant's source documentation. Assignment of IMP should not be recorded in any trial documents or source document.

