## 8.7. Pharmacokinetics

Sampling for pharmacokinetics will be sparse. Thus, the test IMP pharmacokinetic samples will be analyzed using a population pharmacokinetic approach and will be reported separately from the clinical study report (CSR).

Samples from participants who receive test IMP will be analyzed for fremanezumab using a validated method. Samples from participants who receive placebo IMP will not be analyzed.

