#### 9.1.4. Per-Protocol Analysis Set

The per-protocol analysis set will consist of all participants in the FAS who have completed the trial without any important deviations, such as important inclusion/exclusion criteria deviations, important deviations or omissions of the IMP administration, or unexpected drug concentration findings, and who have at least 75% diary compliance after the start of treatment.

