The **monthly average number of days or hours** of efficacy variables (eg, migraine days, days of headache with at least moderate severity, days of headache with any severity, total hours of headache with any severity, total hours of headache with at least moderate severity, days of use of any acute headache medications, days with nausea or vomiting, days with photophobia and phonophobia etc.) **during the 12-week period** after the 1st dose of IMP will be derived and normalized to **28** days equivalent using the following formula.

$$\frac{\sum \text{Days or hours of efficacy variable over the 12 week period}}{\sum \text{Days with assessments recorded in the eDiary for the 12 week period}} \times 28 \quad (1)$$

The **monthly number of days or hours** of efficacy variables **during a 4-week period** after each dose will be derived and normalized to **28** days equivalent using the following formula, where monthly data separated by each visit of IMP dosing will be used.

$$\frac{\sum \text{Days or hours of efficacy variable during the 4 week period}}{\sum \text{Days with assessments recorded in the eDiary for the 4 week period}} \times 28 \quad (2)$$

The **baseline values** will be calculated using all data collected in the run-in period, ie,

$$\frac{\sum \text{Days or hours of efficacy variable during the run - in period}}{\sum \text{Days with assessments recorded in the eDiary for the run - in period}} \times 28 \quad (3)$$

The **percentage of reduction** in the monthly average number of an efficacy variable will be calculated as

$$\frac{\text{baseline value} - \text{postbaseline value}}{\text{baseline value}} \times 100\% \quad (4)$$

where the baseline value is calculated by formula (3) and the postbaseline value in the equation is calculated by formula (1) for the variables **during the 12-week period** or by formula (2) for the variables **during the 4-week period** after each dose for months 1, 2 and 3.

The FAS will be used for all efficacy analyses unless otherwise specified. Summaries will be presented by treatment group as randomized (test IMP or placebo IMP), unless otherwise noted. Descriptive statistics for all efficacy data will be presented by month or visit as appropriate and over 12-week period.

The primary and secondary endpoints analysis will be repeated for the per-protocol analysis set.

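### The per-protocol set's drug-concentration exclusion can in practice reach only participants on test IMP, because placebo samples are not assayed

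*SAP*

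**What the plan says.** SAP 3.4 builds the per-protocol set from FAS participants who completed the trial without important deviations. The examples it lists include "important deviations or omissions of the IMP administration, or unexpected drug concentration findings". Protocol 9.1.4 has the same item, placed beside the diary requirement: "or unexpected drug concentration findings, and who have at least 75% diary compliance after the start of treatment". The criterion is therefore current in both documents.

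Protocol 8.7 sets out who is assayed: "Samples from participants who receive test IMP will be analyzed for fremanezumab using a validated method", and then "Samples from participants who receive placebo IMP will not be analyzed". Protocol 6.6.3 explains how the laboratory can tell the two apart: "Personnel responsible for bioanalysis will be provided with the randomization code to facilitate the analysis".

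SAP 6.1 gives the set its use: "The primary and secondary endpoints analysis will be repeated for the per-protocol analysis set". The same section makes the FAS the default: "The FAS will be used for all efficacy analyses unless otherwise specified". The FAS definition in SAP 3.3 has no concentration criterion.

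**The concern.** A per-protocol repeat is useful as support only if its exclusions are applied alike in both arms. Here one ground rests on a measurement made after randomization and available in one arm. An active participant with an odd drug level can be taken out. A placebo participant treated as assigned has no result that could take them out.

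What is at stake is the credibility of the per-protocol estimates for the primary and secondary endpoints. If the active participants removed are those with little or no drug on board, and they respond less, the active mean is selected upward with no matching selection on placebo. The primary result is not at stake.

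**Working it through.** **The texts side by side.**

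- The exclusion ground needs a concentration result (SAP 3.4, Protocol 9.1.4).
- A concentration result exists only for samples that are assayed, and placebo samples are not (Protocol 8.7). The laboratory holds the randomization code (Protocol 6.6.3).
- Neither document gives a placebo counterpart, a threshold, a direction, or a definition of an unexpected finding.
- Protocol 8.7 turns on what a participant received, so a placebo-randomized participant known to have been given test IMP could be assayed. That person would already be excludable for an IMP administration deviation, so the concentration ground adds nothing there. An undetected kit mix-up in the placebo arm would not surface through this criterion.

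**The plan's own figure (SAP 2.4, Protocol 9.8).** The inputs are a difference of 1.7 days, SD 4.92, two-sided alpha 0.05 and 80% power.

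- n per arm = 2 × (1.960 + 0.842)² × 4.92² / 1.7² = 131.5, so 132, against 133 stated. Power at 133 per arm is 80.4%.
- 133 / 0.96 = 138.5, so 139 per arm and 278 in total, as stated.
- Standard error of the difference at 133 per arm = 4.92 × √(2/133) = 0.60 days.

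**Illustrative shift.** The documents give no rate of concentration-based exclusion, so the rates are assumptions. Let a fraction f of the active arm be removed and none of the placebo arm, and let those removed do m days worse than the active mean. The remaining active mean then improves by f × m / (1 − f). A placebo-like response means m = 1.7.

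- 4 of 133 (3%): 0.0301 × 1.7 / 0.9699 = 0.053 days, about 9% of the standard error.
- 7 of 133 (5%): 0.0526 × 1.7 / 0.9474 = 0.094 days, about 16% of the standard error.

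The range over wider assumptions, in days:

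| f | m = 1.7 | m = 4.92 (1 SD) |
|---|---|---|
| 1% | 0.02 | 0.05 |
| 5% | 0.09 | 0.26 |
| 10% | 0.19 | 0.55 |

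If there were no true difference before exclusion, the two-sided rejection rate of the per-protocol test would rise from 5.0% to 5.3% (f = 5%, m = 1.7) or 7.1% (f = 5%, m = 4.92). This requires drug level to be related to outcome for some reason other than a drug effect.

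If those removed do better than the active mean, m is negative and each shift changes sign. If removal is unrelated to outcome (m = 0) there is no shift, and power at 1.7 days falls only to 79.4% at f = 5% or 78.3% at f = 10%.

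**The case against.** The strongest case on the other side has four parts.

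- **No decision rests on this set.** The FAS carries the primary analysis, and the fixed sequence in SAP Section 7 contains no per-protocol test. This stands, and it limits the weight of the point.
- **The direction is not known.** A reader might infer that the exclusion always favors fremanezumab. The documents do not support that. An unexpected finding could be a high level, or drug detected in the visit 2 sample, which is taken before dosing (Protocol 13.9).
- **Dosing errors are not hidden in the placebo arm.** A reader might infer that a wrong kit given to a placebo participant cannot be found. Kits are numbered and assigned by the IRT at each visit (Protocol 6.6.1), and any administration outside the protocol must be reported as a deviation (Protocol 8.3.7). A known error in either arm already falls under the IMP-administration item. Only an undetected error is out of reach.
- **The criterion may exclude few participants or none.** During the trial, concentrations are released so that "a dummy participant identifier will be linked to the concentration data of an individual participant". Deviations are reviewed before database lock (SAP 5.9), while the sponsor's clinical personnel remain blinded until lock (SAP 2.2). The documents describe no route from a concentration result to per-protocol membership.

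The last part cuts both ways. Since a result exists only for participants on test IMP, linking it to a participant before lock would reveal treatment. Linking it afterwards would settle membership unblinded. None of the four parts supplies the missing placebo counterpart.

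**Conclusion.** The point holds as a limited one. The per-protocol definition contains a post-randomization exclusion that in practice can act on one arm only, and nothing elsewhere in the documents balances it. The bias is toward benefit only if those removed are under-exposed and respond less; otherwise it may be absent or reversed.

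Under a placebo-like response and an assumed 3% to 5% removal, the shift is small beside sampling error. It becomes material only under larger assumed departures, such as 0.26 days when 5% are removed who do a full SD worse. The 1.7 days used in the illustration was planned for headache days of at least moderate severity, not for migraine days, which is now the primary endpoint. A reader might infer that the main efficacy conclusion is in doubt; it is not, because this criterion does not touch the FAS analysis or the testing hierarchy.

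**What to change.** Delete the concentration item from the per-protocol definition in SAP 3.4 and record the departure from Protocol 9.1.4 in SAP Section 15. Rely on the IMP-administration criterion, which is recorded in both arms. The SAP introduction lets the SAP prevail where the two documents differ.

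The note to file appended to the SAP, dated 29 May 2025, says that the trial analysis was conducted. If the per-protocol sets have been formed, the change is post hoc. In that case, report by arm how many participants this criterion removed, repeat the per-protocol analyses without it, and disclose both results in the CSR.

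The cost is one clause, one entry in Section 15 and at most one rerun, with no new data. What is lost is a check on undetected dosing errors in the active arm; showing the results both ways keeps it. Assaying placebo samples under the same predefined rule would also restore symmetry, but it needs laboratory work.

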4. GENERAL ISSUES FOR DATA ANALYSIS

4.1. General

Descriptive statistics for continuous variables include n, mean, standard deviation (SD), standard error (SE), median, minimum, and maximum. Descriptive statistics for categorical variables including participant counts, percentages and missing category will be displayed as appropriate.

Summaries of potentially clinically significant abnormal values will include all postbaseline values (including scheduled, unscheduled, and early termination visits).

4.2. Specification of Baseline Values

Participants will complete electronic headache diary entries daily for the 28-day run-in period, subjectively rating their headaches as mild, moderate, or severe and enter headache information (ie, occurrence of headache, duration of headache, maximum severity of headache, and acute headache medication use) about the previous day into the electronic headache diary device. If the participant is unable to complete the diary themselves then a parent/caregiver will complete the diary for them. Headache severity is collected in the diary on an 11-point numerical rating scale where mild is defined as a rating of 1-3, moderate as 4-6 and severe as 7-10. If the run-in period is greater or less than 28 days, the baseline values for calculating the change from baseline of the monthly values of the efficacy variables will be normalized to **28** days.

The efficacy baseline values during the 28-day run-in period derived from the e-diary include

- total number of migraine days
- total headache days of at least moderate severity
- total number of days of use of any acute headache medication
- total headache days of any severity
- total number of days of use of acute headache medications (triptans and ergot compounds, NSAIDs or paracetamol) for the group of participants who use acute headache medications at baseline
- total number of days with nausea or vomiting
- total number of days with photophobia and phonophobia

Other efficacy baseline values that will be measured on day 1 before the 1st IMP administration include

- disability score, as measured by the PedMIDAS assessment ([Appendix C](#))
- quality of life, as measured by the PedsQL questionnaire ([Appendix D](#))

Otherwise, baseline value will be the last non-missing value prior to the 1st dose of IMP, unless otherwise noted.

4.3. Handling Withdrawals and Missing Data

If a participant has ≥ 10 days of the e-diary data after 1st dose of IMP, his/her monthly average number of days/hours of efficacy variables ***during the 12-week period*** or monthly number of days/hours of efficacy variables ***during the 4-week period*** will be prorated to **28** days.

Participants who have <10 days/hours of diary data will be excluded from the full analysis set.

Multiple imputation (MI) method will be applied on the primary variable as sensitivity analyses. The methods will be described in detail in Section [6.2.3](#).

A participant's monthly number of days/hours of efficacy variables ***during the 4-week period*** after each dose of IMP will be calculated for months 1, 2, and 3. If a participant has missing diary days in a month, the following method will be used to handle the missing data.

- If the participant has 10 or more days of e-diary data for a month, the monthly number of days/hours of efficacy variables will be prorated to **28** days for that month.
- If the participant has less than 10 days of e-diary data for a month, the monthly number of days/hours of efficacy variables will be considered as missing.

4.4. Trial Days and Visits

Trial days will be numbered relative to the 1st day of IMP administration. The start of treatment (visit 2 or day 1) is defined as the date on which a participant takes the 1st dose of IMP, as recorded on the IMP administration CRF. Days will be numbered relative to IMP start (ie, ..., -2, -1, 1, 2, ...; with day 1 being the start of IMP and day -1 being the day before the start of IMP).

The 4-week (28-day) visit windows for the e-diary based efficacy endpoints will be determined based on the actual dosing day. The run-in phase is defined as day -28 to -1 before the 1st injection on day 1. Treatment phase including month 1, 2 and 3 is from the beginning of the 1st injection of IMP to visit 5/day 84 or the end of treatment visit. The 3-month visit windows are separated by each dosing date/time. Month 1 is from the date/time of the 1st dose of IMP administration on day 1 to the date/time just before the 2nd dose. Month 2 is from the date/time of the 2nd dose to the date/time just before the 3rd dose. Month 3 is from the date/time of the 3rd dose to the end of the trial on day 84 approximately. If the Month 2 or Month 3 dosing day is missed, then the dosing day is considered to be previous dosing day +28 days.

Throughout this document, all by month efficacy summaries for the headache data will refer to these visit windows.

For all other by visit summaries, except for triplicate ECG assessments (see Section [8.9](#) for further details), if there are multiple assessments at a postbaseline visit then the last non-missing assessment at that visit will be used for the summary. This includes assessments at the scheduled and unscheduled visits.

Last Assessment for analyses and summaries is the last observed postbaseline data. For participants who withdraw from the trial, data at the early termination visit will be excluded from the by-visit summaries but will be included in the endpoint summaries.

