- l. In the judgment of the Investigator, the participant has an abnormal finding on the baseline 12-lead ECG considered clinically significant.
- m. In the judgment of the Investigator, the participant has a significantly abnormal finding during the 28-day baseline period, including hematology, blood chemistry,

coagulation tests, or urinalysis values/findings (abnormal tests may be repeated for confirmation).

- n. The participant has hepatic enzymes (alanine aminotransferase [ALT], aspartate aminotransferase [AST], alkaline phosphatase [ALP]) more than  $1.5 \times$  the upper limit of normal (ULN) during the 28-day baseline period, after confirmation in a repeat test, or suspected hepatocellular damage that fulfills the criteria for Hy's law.
- o. The participant has serum creatinine more than  $1.5 \times$  the ULN, clinically significant proteinuria (urine dipstick +4), an estimated glomerular filtration rate (eGFR) of  $<75$  mL/min/1.73m^2, as calculated by the revised Schwartz formula (eGFR=[0.413×Ht]/serum creatinine), or evidence of renal disease during the 28-day baseline period.
- p. The participant has any history of alcohol or drug abuse. The definition of alcohol or drug abuse, including marijuana, is based on the Investigator's clinical judgement.
- q. In the judgment of the Investigator, the participant cannot fully participate in or successfully complete the trial for its full duration for any of the following reasons:
  - The participant is mentally or legally incapacitated, or unable to give assent/consent for any reason.
  - The participant is in custody due to an administrative or a legal decision or is in residential treatment.
  - The participant /caregiver is unable to be contacted in case of emergency.
  - The participant has any other condition, which, in the opinion of the Investigator, makes the patient inappropriate for inclusion in the trial.
  - The participant is a relative of a trial center or Sponsor employee who is directly involved in the trial.
- r. Vulnerable participants (eg, people kept in detention) whose vulnerability is based on a condition other than the age required for trial eligibility.
- s. The participant received a live attenuated vaccine (eg, intranasal flu vaccine, and measles, mumps, and rubella vaccine) within the 12-week period prior to screening.

**Note:** If a medical need arises during the trial, the participant may receive a live attenuated vaccine.

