### **8.3.2. Vital Signs**

Vital signs (pulse, systolic and diastolic blood pressure (BP), temperature, and respiratory rate) will be measured at any time during the visit, as detailed in [Table 1](#). The method for measuring temperature in an individual participant must be the same at each time point.

Before pulse and BP are measured, the participant must be in a supine or semi-erect/seated position and resting for at least 5 minutes. The same position and arm should be used each time vital signs are measured for a given participant. For any abnormal vital sign finding, the measurement should be repeated as soon as possible. Any vital sign value that is judged by the Investigator as a clinically significant change (worsening) from a baseline value will be considered an adverse event, recorded on the source documentation and transcribed onto the CRF, and monitored as described in Section 8.4.5.

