### **8.3.4.1. Serum Chemistry, Hematology, Coagulation, and Urinalysis**

All clinical laboratory test results outside of the reference range will be judged by the Investigator as belonging to one of the following categories:

- abnormal and not clinically significant
- abnormal and clinically significant

A laboratory test result that is judged by the Investigator as clinically significant will be recorded both on the source documentation and the CRF as an adverse event and monitored as described in Section 8.4.5. An adverse event may include a laboratory or diagnostic test abnormality (once confirmed by repeated testing) that results in the withdrawal of the participant from the trial, the temporary or permanent withdrawal of IMP or medical treatment, or further diagnostic work-up. (Note: Abnormal laboratory or diagnostic test results at the screening visit that preclude a participant from entering the trial or receiving IMP are not considered adverse events.)

In addition, potentially clinically significant values will be predefined by the Sponsor for selected laboratory parameters and will be detailed in the statistical analysis plan.

Clinical laboratory tests (serum chemistry, hematology, coagulation, and urinalysis) will be performed at the time points detailed in [Table 1](#). In case of suspected hepatitis, HIV, or Lyme disease, a blood sample may be taken at screening at the discretion of the Investigator. Baseline is screening (visit 1). Clinical laboratory tests will be performed using the central laboratory. Specific laboratory tests to be performed are listed in Section 13.2. Note, reflex tests (eg, red blood cell [RBC] shapes, RBC morphology, and other microscopic findings) may be triggered automatically.

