#### Elevation of Either ALT or AST to $\geq 3 \times$ ULN

Confirmation is required prior to IMP discontinuation in cases of elevation of either ALT or AST  $\geq 3 \times$  ULN (Note: In cases of elevation of ALT or AST  $\geq 8 \times$  the ULN, no confirmation is required prior to IMP discontinuation, but the assessments below should be performed). The following procedures should be followed:

- The day in which the abnormal value is received from the laboratory will be considered as day 0.
- The Investigator should repeat the test for confirmation purposes (this may be performed in a local laboratory along with complete blood count [CBC] and differential to assess for eosinophilia. In general, in case a blood sample is sent to a local laboratory, the following assessments [and reference ranges] are mandatory: ALT [serum glutamic pyruvic transaminase], AST [serum glutamic oxaloacetic transaminase], ALP, total bilirubin, CBC [with differential for eosinophil count, separate tube], and INR [separate tube; not to be sent in a confirmatory test]). The Investigator should also question the participant regarding symptoms.

---

 In case total bilirubin is  $>$ ULN, then direct bilirubin will be checked.

 Thorough medical history with a focus on liver disease: personal or family history of liver disease; personal history of a systemic disease with potential liver involvement; exposure to alcohol, medications (prescription or over the counter), herbal preparations, dietary supplements, recreational drugs, special diets, or environmental chemical agents; potential exposure to infectious agents (eg, travel to developing countries, history of potential exposure to blood or blood products, high-risk sexual relations); and any additional information deemed relevant by the Investigator. Physical examination, including signs of chronic liver disease.

The abnormality will be regarded as confirmed in each of the following scenarios:

- the baseline value was within the normal range and ALT or AST is still  $\geq 3 \times$  the ULN
- the baseline value was above the ULN and ALT or AST is  $\geq 2 \times$  the baseline value

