8.6. Clinical Laboratory Tests

Clinical laboratory tests (serum chemistry, hematology, coagulation, and urinalysis) will be performed using the central laboratory at the time points detailed in the trial protocol. Specific laboratory tests to be performed are listed below in [Table 3](#).

Table 3: Clinical Laboratory Tests

Serum chemistry	Hematology and coagulation	Urinalysis
Calcium	Hemoglobin	Color and appearance
Phosphate	Hematocrit	Protein
Sodium	RBC count	Glucose
Potassium	RBC indices	Ketones
Chloride	mean corpuscular volume	Blood
Creatinine	mean corpuscular hemoglobin concentration	Leukocyte esterase
Glucose	RBC distribution width	Nitrite
BUN	Platelets	Bilirubin
ALT	Leukocytes	pH
AST	neutrophils	Specific gravity
LDH	lymphocytes	Microscopic tests
GGT	eosinophils	bacteria
Alkaline phosphatase	monocytes	erythrocytes
Creatine phosphokinase	basophils	leukocytes
Carbon dioxide	Prothrombin time	crystals
Magnesium	Partial thromboplastin time	casts
Protein	INR	
Albumin		
Bilirubin (total and direct)		

ALT=alanine aminotransferase; AST=aspartate aminotransferase; BUN=blood urea nitrogen; GGT=gamma-glutamyl transpeptidase; INR=International Normalized Ratio; LDH=lactate dehydrogenase; RBC=red blood cell.

Laboratory tests results and changes from baseline for chemistry, hematology, urinalysis, and coagulation laboratory tests will be summarized by visits for each treatment group using descriptive statistics. Shifts (below, within, and above the normal range) from baseline to each visit and Last Assessment will be summarized using participant counts. Listings of all individual participants' laboratory test results will be presented.

All clinical laboratory test results outside of the reference range will be judged by the Investigator as belonging to one of the following categories:

- abnormal and not clinically significant
- abnormal and clinically significant

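### SAP 4.4 lets an abnormality-prompted repeat replace the scheduled laboratory or vital-sign value, so laboratory shift tables can undercount out-of-range results and real mean changes can be slightly attenuated

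*SAP*

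**What the plan says.** **Selection rule.** SAP 4.4 covers all by-visit summaries other than the diary data and triplicate ECGs. Where a postbaseline visit has several assessments, "the last non-missing assessment at that visit will be used for the summary. This includes assessments at the scheduled and unscheduled visits". Last Assessment is likewise the last observed postbaseline value. Under SAP 4.2 the laboratory and vital-sign baseline is the last non-missing value before the first dose.

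**What prompts a repeat.**
- Vital signs (Protocol 8.3.2, repeated in SAP 8.8): "For any abnormal vital sign finding, the measurement should be repeated as soon as possible".
- ALT or AST at or above 3x ULN (Protocol 12.2.1): "The Investigator should repeat the test for confirmation purposes (this may be performed in a local laboratory)".
- Other on-treatment laboratory tests (Protocol 8.3.4.1): abnormalities that lead to withdrawal, treatment or further work-up may be adverse events once confirmed by a repeat. There is no general instruction to repeat every out-of-range result.
- Baseline period (Protocol 5.4, criterion m): "abnormal tests may be repeated for confirmation".

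**Displays that use the rule.** SAP 8.6: "Laboratory tests results and changes from baseline for chemistry, hematology, urinalysis, and coagulation laboratory tests will be summarized by visits", and "Shifts (below, within, and above the normal range) from baseline to each visit and Last Assessment will be summarized using participant counts". SAP 8.8 plans values and changes for vital signs, but no shift table.

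**Displays that do not.** SAP 4.1: "Summaries of potentially clinically significant abnormal values will include all postbaseline values", whether scheduled, unscheduled or from early termination. SAP 8.6 lists every individual laboratory result. SAP 8.9 takes the worst ECG finding at a visit and adds an overall worst-value shift.

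**The concern.** Whether a value is replaced depends on the value itself. A normal first result is kept. An abnormal one is more likely to be followed by a second, which on average lies closer to the centre of the distribution even if nothing has changed in the participant. Taking the last value therefore moves the by-visit display toward normal.

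Changes from baseline in laboratory tests and vital signs are named safety endpoints (Protocol 3.1, SAP 1.1), in a paediatric trial without a data monitoring committee. The arm with more abnormal first values has more of them open to replacement, so a true difference between arms would also be shown as smaller than it is. The SAP avoids this for ECG findings by using the worst value, but plans no corresponding worst-postbaseline shift for laboratory tests.

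**Working it through.** The plan states no figure here to reproduce. The check has three steps: match triggers to tables, size the shift-table effect, and size the mean-change effect.

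**1. Which trigger meets which table**

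| Data | Instruction to repeat | By-visit means | Shift table under SAP 4.4 |
|---|---|---|---|
| Vital signs | Every abnormal value | Yes | None planned |
| ALT, AST | At or above 3x ULN | Yes | Yes |
| Other laboratory tests | Confirmation or discretion only | Yes | Yes |
| ECG | Planned triplicate | Excluded from the rule | Worst finding used |

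The strongest trigger (vital signs) meets only means. The shift tables (laboratory) meet a mandatory repeat only for marked transaminase elevations.

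**2. Above-range counts**

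Assumptions not in the documents: first and repeat values are bivariate normal with correlation ρ, the upper limit is the 97.5th percentile (1.96 SD), and a fraction f of first-high values is repeated and assigned to the same visit.

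Let q = P(repeat high | first high). The proportional fall in the above-range count is f × (1 − q).

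| ρ | q | 1 − q | f = 0.10 | f = 0.50 | f = 1 |
|---|---|---|---|---|---|
| 0.50 | 0.185 | 0.815 | 8% | 41% | 81% |
| 0.70 | 0.331 | 0.669 | 7% | 33% | 67% |
| 0.85 | 0.508 | 0.492 | 5% | 25% | 49% |

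Effect on a contrast: suppose 5.0% of first values are high on active and 2.5% on placebo, a difference of 2.5 points. With f = 1 the displayed rates are 1.22% and 0.46% at ρ = 0.50 (difference 0.76), and 2.80% and 1.27% at ρ = 0.85 (difference 1.53). The displayed difference is linear in f:
- f = 0.10: 2.5 − 0.10 × (2.5 − 0.76) = 2.33 points at ρ = 0.50, and 2.5 − 0.10 × (2.5 − 1.53) = 2.40 at ρ = 0.85.
- f = 0.50: 1.63 and 2.01 points.

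**3. Mean changes**

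Simulation of 2,000,000 draws on standardised values. Abnormal values on either side are all repeated, and baseline follows the same last-value rule, as SAP 4.2 provides.

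| Reliability | Mean change, true 0.5 SD | Attenuation | Mean change, no drug effect |
|---|---|---|---|
| 0.5 | 0.441 | (0.5 − 0.441)/0.5 = 12% | 0.00 |
| 0.7 | 0.464 | 7% | 0.00 |
| 0.9 | 0.488 | 2% | 0.00 |

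If only high values count as abnormal and half of them are repeated, the means are 0.481, 0.487 and 0.496, an attenuation of about 4%, 2% and 1%. With no drug effect, if only postbaseline high values are repeated and the baseline is not, the mean change is biased by about −0.03 SD (reliability 0.5) to −0.005 SD (0.9).

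**The case against.** The strongest reply is that the affected tables are not where repeats are required. For laboratory tests the only explicit on-treatment trigger is ALT or AST at or above 3x ULN. A repeat that falls from 3x to 1.5x ULN is still above range in a three-category table. Abnormal values also survive elsewhere: PCS summaries use all values, every laboratory result is listed, and results that the investigator judges clinically significant become adverse events. The summaries are descriptive, with no planned test between arms. Finally, the last value is sometimes the better one, because it may correct a bad reading or show a rising trend.

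Most of this stands, and it limits the point to a minor one. A reader might infer that the by-visit tables lose half to four-fifths of abnormal results, or that a safety signal would disappear. The documents do not support that. The 49% to 81% figure needs every first-high value to be repeated at that visit, which no passage requires for laboratory tests in general. Nor is there a vital-sign shift table to distort.

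Two things remain. SAP Table 4 has no PCS criterion for calcium, phosphate, sodium, potassium, chloride, serum glucose, creatine phosphokinase, carbon dioxide, magnesium, serum protein or albumin. Apart from any adverse-event reports, the means and shift tables are their only planned tabulations. In addition, SAP 4.4 defines windows for diary data only, so it is not stated how a later or local-laboratory repeat is assigned to a visit.

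**Conclusion.** The point holds as a minor one about descriptive safety reporting. The rule selects on outcome, and its direction is toward normal. Laboratory shift tables can undercount out-of-range results; laboratory and vital-sign mean changes can be slightly attenuated when there is a real drug effect.

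The size turns on the fraction of abnormal values repeated, which is unknown. With correlation 0.5 to 0.85, above-range counts fall by about 5% to 8% at 10% repeated and 25% to 41% at 50%; 49% to 81% is an upper bound at 100%. Mean changes lose about 2% to 12% for an assumed 0.5 SD shift with every abnormal value repeated, and almost nothing without a drug effect. All of these rest on normality and on repeats being assigned to the same visit. The primary, secondary efficacy and multiplicity analyses are not affected.

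**What to change.** 1. SAP 4.4: for by-visit means, changes from baseline and laboratory shifts, use the scheduled assessment. Use a repeat or unscheduled value only if the scheduled one is missing or documented as invalid.
2. SAP 4.2: apply the same selection to the laboratory and vital-sign baseline. Changing 4.4 alone would pair a repeat-selected baseline with a scheduled postbaseline value.
3. SAP 8.6: add a worst-postbaseline laboratory shift over all values, as SAP 8.9 does for ECG findings. This also covers a result that worsens on repeat.
4. Keep PCS summaries and listings on all values, as planned.

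The cost is a few sentences, one derivation flag and one extra table. The downside is that an isolated spurious reading may remain in a by-visit mean, although its repeat is still available in the data. The note to file at the end of the SAP describes the trial analysis as already conducted. If the safety tables exist, the revised versions can be added to the clinical study report as labelled additional analyses.
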